### **8.3 Treating the Patient**

#### **8.3.1 Patient Numbering**

Each patient will be assigned a Patient ID Number (PID) by the site after the patient provides written informed consent. Each patient is uniquely identified in the study by a combination of the study number, site number and the patient's disease code.

- The first 3 digits will designate the study number, as assigned by Allakos (206 for this study).
- The next 3 digits will designate the site number, as assigned by Allakos.
- The last 3 digits will designate the disease code and order of consent at the site.
  - Disease codes are as follows: 1 = CholU, 2 = UF, 3 = CSU (Xolair Naïve), and 4 = CSU (Xolair Failure)
  - The first patient consented at each site will be assigned their disease code + “01”, and subsequent subjects will be assigned consecutive numbers based on consent order at the site (e.g., the second patient consented at the site will be assigned their disease code + “02”, and the third patient consented at the site will be assigned their disease code + “03”, etc.)

**Example:** For example, Site 003 consented 4 patients. The first patient has CSU (Xolair Naïve), the second patient has UF, the third patient has CholU, and the fourth patient has CSU (Xolair Failure). The first patient will be assigned PID 206-003-301, the second patient assigned PID 206-003-202, the third patient assigned PID 206-003-103, and the fourth patient assigned PID 206-003-404.

Once assigned to a patient, a PID number will not be reused. The patient will maintain the same PID number throughout the entire study except if the patient fails the first screening. If a patient signs the ICF but does not meet the inclusion/exclusion criteria, the patient will be considered a screen failure. The patient can be re-screened one additional time during the clinical trial.

However, if this occurs the site will assign the patient a new PID at the subsequent screening visit. If the ICF has been signed within 30 days and there are no new revisions, a new ICF is not necessary.

### **8.3.2 Formulation of AK002**

AK002 is a humanized non-fucosylated IgG1 monoclonal antibody directed against Siglec-8.

AK002 Drug Product is supplied as a sterile liquid in a single-use 10R glass vial with a fill volume of not less than 10 mL. The AK002 formulation is [REDACTED] (use [REDACTED] for dose prep) AK002 in [REDACTED]

[REDACTED] pH 6.0, in sterile water for injection.

Allakos, Inc. will supply the investigational site with AK002. AK002 must not be shaken or frozen. AK002 will be stored by the study site at 2–8°C under lock, pending drug preparation. Access will be restricted to designated study pharmacy staff. All clinical supplies will be temperature controlled and monitored. If the temperature of study drug storage in the clinic/pharmacy exceeds or falls below this range, this will be reported to the Principal Investigator and captured as a deviation.

The NaCl 0.9% for IV injection is commercially available and will be ordered as needed. The NaCl 0.9% should be stored at room temperature.

Study drug will be administered by IV infusion using an infusion pump. Dose preparation and administration details are included in the study Pharmacy Manual.

### **8.3.3 Supply of AK002 to the Investigational Site**

The Sponsor (or designee) will ship study drug to the investigational sites. The initial study drug shipment will be shipped after site activation (i.e., after all required regulatory documentation has been received by the Sponsor and a contract has been executed). Subsequent study drug shipments will be made by the Sponsor or designee.

Each vial will be labeled with the required investigational use statement, lot number, and directions for storage.

### **8.3.4 Preparation of Study Drug**

Please refer to the Pharmacy Manual for additional details regarding study drug preparation.

The amount of AK002 to be administered will be calculated based on the patient's body weight determined within 24 hours of each infusion.

The calculated amount of study drug based on body weight will be diluted with 0.9% NaCl for IV injection.

The final combined volume of the IV bag of study drug + 0.9% NaCl will be **120 mL**.

**Note:** Exactly **100 mL** of the calculated dose of study drug will be administered to the patient. The extra 20 mL is to be used to prime the IV infusion line during the preparation of the IV line at the bed side.

It is recommended that each dose of 120 mL is prepared in an empty medication delivery bag.

For all 6 doses (0.3 mg/kg on Day 1, 1 mg/kg on Day 29 and Day 57, and 3 mg/kg on Day 85, Day 113, and Day 141), 100 mL dose of study drug will be infused over approximately 4 hours.

After each dose, the patient will be monitored for at least 4 hours after IV administration. At the discretion of the PI, monitoring may be extended for an additional 24 hours.

Detailed instructions for preparing the drug are in the Pharmacy Manual.

### 8.3.5 AK002 Administration

Premedication with oral doses of acetaminophen/paracetamol (1000 mg) and cetirizine (10 mg) will be given 1 hour prior to the infusion for doses 1 and 2. Any premedication for subsequent doses will be based on the Investigator's discretion. AK002 will be infused through a peripheral vein IV set. The IV line will be kept open before and after the infusion with sufficient quantities of 0.9% NaCl to assure patency.

Based on the patient's weight, the designated clinical staff will prepare the appropriate dilution of AK002 at 0.3 mg/kg (for Day 1), 1 mg/kg (for Day 29 and Day 57), and 3 mg/kg (for Day 85, Day 113, and Day 141) for IV administration. Appropriate aseptic technique will be used, and the study drug will be prepared according to the Pharmacy Manual for AK002.

The site's designated clinical staff will keep accurate and current accounting of the preparation and dose calculation of study drug for each patient, with source, quantities of study medication dispensed, used, and returned. All dosage calculations will be documented on the source documents. A study drug receipt, dispensation, and disposition log will be maintained by the pharmacist on the Investigational Drug Accountability Record. A study monitor will verify entries on these documents throughout the course of the study.

Specific instructions on administration are detailed in the Pharmacy Manual. In general, all doses i.e., 0.3 mg/ kg at Day 1, 1 mg/kg at Day 29 and Day 57, and either 1 mg/kg or 3 mg/kg (depending on UCT score) at Day 85, Day 113, and Day 141 will be given as an IV infusion over approximately 4 hours, following an observation period of 4 hours.

All dosages prescribed and dispensed to the patient and all dose changes during the study must be recorded on the appropriate eCRF.

Subjects in the CholU, UF, and CSU-XOLAIR® (omalizumab) failure cohorts who received all 6 infusions of AK002, were followed through Day 155, and demonstrated severe symptoms of urticaria following discontinuation of treatment will be eligible to receive extended dosing with up to 12 additional doses of AK002 (see [Appendix 2](#)).

For extended dosing, subjects must have a baseline (Day 1) UCT of  $\leq 5$  and a week 22 (Day 155) UCT of  $\geq 12$  (Complete Response). They must have a UCT of  $\leq 5$  between Day 155 and Day 309 (i.e., within 6 months from last dose).

All subjects that decide to receive extended dosing will start with a dose of 0.3 mg/kg, followed by possible dose increases to 1 mg/kg and 3 mg/kg for subsequent infusions.

The Investigator in consultation with the Medical Monitor may increase the dose to 6 mg/kg and then to 10 mg/kg if they think that the patient has not received benefit from the lower doses.

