Dose and Route of Administration	
Up to 6 doses of AK002 will be given over the course of the study. AK002 will be administered as an intravenous (IV) infusion at a dose of 0.3 mg/kg given over a period of approximately 4 hours on study Day 1 (Dose 1). If well tolerated, dose will be increased to 1 mg/kg, given over a period of 4 hours on study Day 29 (Dose 2) and Day 57 (Dose 3) (<math>\pm</math>2 days). For Doses 4, 5, and 6 on Day 85, Day 113, and Day 141, respectively, dose will be increased to 3 mg/kg if patient has UCT score of <math><12</math>, and/ or at the discretion of the Investigator in consultation with the Allakos Medical Monitor. If the UCT score <math>\geq 12</math> and if the Investigator in consultation with the medical monitor feels that the patient has received adequate symptom improvement, then the patient will continue to receive 1 mg/kg dose.
 
Subjects in the CholU, UF, and CSU-XOLAIR® (omalizumab) failure cohorts who received all 6 infusions of AK002, were followed at least through Day 155, and demonstrated severe symptoms of urticaria following the last dose of treatment will be allowed the option to receive extended dosing with up to 12 additional doses of AK002 (see Appendix 2). They will have to be treated with extended dosing within 6 months of last dose.

Dose and Route of Administration cont.	
All subjects that decide to receive extended dosing will start with a dose of 0.3 mg/kg, followed by possible dose increases to 1 mg/kg and 3 mg/kg for subsequent infusions.
 
The Investigator in consultation with the Medical Monitor may increase the dose to 6 mg/kg and then to 10 mg/kg if they think that the patient has not received benefit from the lower doses.
 
The amount of AK002 to be administered will be calculated based on the patient's body weight determined within 24 hours of each infusion. The calculated amount of AK002 (████████) based on body weight will be diluted with 0.9% NaCl for IV injection. Final combined volume of each IV bag of AK002 + 0.9% NaCl will be 120 mL.
 
Note: Exactly 100 mL of the calculated dose of AK002 will be administered to each patient. The extra 20 mL is to be used to prime the IV infusion line during the preparation of the IV line at the bed side.
 
It is recommended that each dose of 120 mL is prepared in an empty medication delivery bag. The doses for the extension study are outlined in Appendix 2.

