**Table 1 Study Outline**

Screening	Treatment						Follow-up		
	0.3 mg/kg	1 mg/kg	1 mg/kg	3 mg/kg*	3 mg/kg*	3 mg/kg*	1	2	3
Visit 1	Visit 2	Visit 3	Visit 4	Visit 5	Visit 6	Visit 7	Visit 8	Visit 9	Visit 10
Week -4	Week 0	Week 4	Week 8	Week 12	Week 16	Week 20	Week 22	Week 24	Week 28
Day -28	Day 1	Day 29	Day 57	Day 85	Day 113	Day 141	Day 155	Day 169	Day 197

\* Increase to 3 mg/kg if UCT score is <12 and/or at the discretion of the Investigator in consultation with the Allakos Medical Monitor. If UCT score is ≥12, and if the Investigator in consultation with the Medical Monitor feels that the patient has experienced adequate symptom improvement, then continue with the 1 mg/kg dose.

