## **8. Study Treatment**

### **8.1 Investigational Treatment**

AK002 will be administered as an intravenous (IV) infusion at a dose of 0.3 mg/kg given over a period of approximately 4 hours on Study Day 1. If well tolerated, dose will be increased to 1 mg/kg, given over a period of approximately 4 hours on study Day 29 and Day 57 ( $\pm 2$  days). Dose will be increased to 3 mg/kg on Days 85, 113, and 141 ( $\pm 2$  days) if the UCT score is <12 and/ or at the discretion of the Investigator in consultation with the Allakos Medical Monitor. If the UCT score  $\geq 12$ , and if the Investigator in consultation with the medical monitor feels that the patient has received adequate symptom improvement, patient will remain at the 1 mg/kg dose. All doses will be given over a period of approximately 4 hours. The duration of infusion and the rate at which the infusion is given may be adjusted based on Investigator discretion.

The amount of AK002 to be administered will be calculated based on the patient's body weight determined within 24 hours of each infusion.

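### The dilution sentence in Protocol 8.3.5, and secondarily the parenthesis in 8.3.4, list 3 mg/kg for Days 85, 113 and 141 without the rule in 8.1 that keeps some subjects at 1 mg/kg

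*Protocol*

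**What the plan says.** **Dosing rule.** Protocol 8.1 starts at 0.3 mg/kg on Day 1 and moves to 1 mg/kg on Days 29 and 57 if the first dose was well tolerated. On Days 85, 113 and 141 the dose rises to 3 mg/kg if UCT is below 12, and/or at the Investigator's discretion after consulting the Medical Monitor. If UCT is 12 or more and they consider the improvement adequate, the "patient will remain at the 1 mg/kg dose". The synopsis says the same ("then the patient will continue to receive 1 mg/kg dose"), as does the Table 1 footnote ("then continue with the 1 mg/kg dose"). Table 3 note r, Section 10.3 and SAP 3.2.1 also keep such a subject at 1 mg/kg.

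**Preparation text.** The second paragraph of 8.3.5 tells clinic staff which dilution to make up: 0.3 mg/kg for Day 1, then "1 mg/kg (for Day 29 and Day 57), and 3 mg/kg (for Day 85, Day 113, and Day 141) for IV administration". Section 8.3.4 lists all six doses in a parenthesis that ends "and 3 mg/kg on Day 85, Day 113, and Day 141), 100 mL dose of study drug". Neither mentions UCT, and neither allows 1 mg/kg on the last three dosing days.

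**Same section, later paragraph.** Two paragraphs further on, 8.3.5 describes the late infusions as "either 1 mg/kg or 3 mg/kg (depending on UCT score) at Day 85, Day 113, and Day 141".

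**Extension.** The corresponding preparation sentence in Appendix 2 gives 1 or 3 mg/kg for the later doses and names UCT score and Investigator discretion as the deciding factors.

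**The concern.** The 8.3.5 sentence is an instruction to the people who make up the infusion, not background, and it is keyed only to body weight and study day. A reader who stops there would prepare 3 mg/kg for everyone from Day 85. Section 8.3.6 then says that dose adjustments are not allowed and does not point back to the UCT rule, so nothing nearby prompts a check.

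At stake is the dose given to a responder, the subject whom the design means to hold at 1 mg/kg. The omission also looks accidental: Appendix 2 uses nearly the same sentence for the extension and includes the choice.

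**Working it through.** The protocol states no figure to reproduce. The check compares every statement of the dose for Days 85, 113 and 141, then works out what literal use of the short wording would do.

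**Step 1. Side-by-side reading**

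| Place | Dose on Days 85, 113, 141 | 1 mg/kg branch present? |
|---|---|---|
| Protocol synopsis | 1 or 3 mg/kg | Yes |
| Protocol Table 1 with footnote | 1 or 3 mg/kg | Yes, in the footnote |
| Protocol 8.1 | 1 or 3 mg/kg | Yes |
| Protocol Table 3, note r | 1 or 3 mg/kg | Yes |
| Protocol 10.3 | 1 or 3 mg/kg | Yes |
| SAP 3.2.1 | 1 or 3 mg/kg | Yes |
| Protocol 8.3.5, later paragraph | 1 or 3 mg/kg by UCT | Yes |
| Protocol Appendix 2, matching sentence (extension) | 1 or 3 mg/kg | Yes |
| Protocol 8.3.5, dilution sentence | 3 mg/kg | **No** |
| Protocol 8.3.4, parenthesis | 3 mg/kg | **No** |
| Protocol 6.3.1 | 3 mg/kg | No, but this is rationale |

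Section 6.3.1 explains the choice of regimen and instructs nobody, so it is not counted as a fault. The two remaining places without the branch both concern preparation or infusion.

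**Step 2. Effect per infusion if read literally**

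For a subject who should stay at 1 mg/kg, the ratio of prepared to intended dose is 3 / 1 = 3. At an assumed 70 kg, that is 3 × 70 = 210 mg instead of 1 × 70 = 70 mg. Eligibility requires a weight below 125 kg; at that limit it is just under 375 mg instead of just under 125 mg.

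**Step 3. Effect over the six doses**

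- Doses 1 to 3, common to all: 0.3 + 1 + 1 = 2.3 mg/kg.
- Literal schedule: 2.3 + 3 × 3 = 11.3 mg/kg.

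| Late doses that should stay at 1 mg/kg | Intended total (mg/kg) | Excess if read literally (mg/kg) |
|---|---|---|
| Three | 2.3 + 3 × 1 = 5.3 | 11.3 − 5.3 = 6.0 |
| Two | 2.3 + 2 × 1 + 3 = 7.3 | 11.3 − 7.3 = 4.0 |
| One | 2.3 + 1 + 2 × 3 = 9.3 | 11.3 − 9.3 = 2.0 |

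These totals are hypothetical. They assume that staff follow the dilution sentence in place of the dose chosen under 8.1. Neither document uses a cumulative mg/kg total for any purpose.

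**Step 4. Who could be affected**

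Only subjects on the six-dose schedule with UCT of 12 or more, judged adequately improved, whom the Investigator and Medical Monitor would hold at 1 mg/kg. The documents give no count or expected share.

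**The case against.** The strongest reply is that nobody reading the protocol as a whole could be misled. The rule appears in the synopsis, the Table 1 footnote, 8.1, Table 3 note r, 10.3 and SAP 3.2.1, and again within 8.3.5. The Investigator chooses the dose after consulting the Medical Monitor, and staff prepare what is prescribed. The paragraph with the dilution sentence also defers to the Pharmacy Manual, which is not available here and may state the rule. Moreover, 3 mg/kg is permitted at UCT of 12 or more on discretion, so giving it is not wrong in every such case. The 8.3.4 parenthesis mainly labels the doses; its sentence is about infusion volume and duration.

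Most of this stands. It limits the likelihood of harm and makes 8.3.4 the secondary location. It does not make the 8.3.5 sentence correct, since that sentence tells staff what to prepare and leaves out one of the two permitted doses.

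Three stronger readings are tempting, and the documents do not support them:

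- **That the dosing rule is undefined, or that responders will in practice get 3 mg/kg.** The rule is defined repeatedly, and the dose decision rests with named roles rather than with preparing staff.
- **That actual dosing could not be reconstructed.** Section 8.3.5 requires that "all dose changes during the study must be recorded on the appropriate eCRF", so a departure would be visible in the data.
- **That the SAP imposes a conflicting dosing rule.** SAP 3.2.1 adds that 1 mg/kg must have been well tolerated before the step to 3 mg/kg, whereas Protocol 8.1 attaches that condition only to the previous step ("If well tolerated, dose will be increased to 1 mg/kg"). The wording does differ, but Protocol 13 gives the SAP precedence for analyses, not for dosing, and no analysis in SAP Section 7 uses the phrase. It is a separate clarification query.

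**Conclusion.** The inconsistency is real and minor. The dilution sentence in 8.3.5 is wrong as written because it omits the 1 mg/kg branch of 8.1; the 8.3.4 parenthesis repeats the omission with less force. Confidence in the textual finding is high, since it rests on direct comparison.

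Its size is a threefold dose at each affected infusion, with a hypothetical maximum of 6.0 mg/kg extra across three infusions. Both figures assume literal use of the short wording for a subject who should stay at 1 mg/kg. How many subjects that could involve cannot be derived from the documents.

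One likely limit on the count is an inference only. SAP 3.1 places the endpoint for subjects enrolled under Amendment 2.1 at Week 10, two weeks after their last dose. That puts the last dose at Week 8 (Day 57), so these subjects would have had no infusion on the three days in question. The documents do not say whether any of them later moved to the six-dose schedule.

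**What to change.** In the 8.3.5 dilution sentence and the 8.3.4 parenthesis, replace the bare 3 mg/kg for Days 85, 113 and 141 with the choice of 1 or 3 mg/kg, decided by UCT score and Investigator discretion, and refer to Section 8.1. Appendix 2 already has a suitable clause. Check that the Pharmacy Manual states the same rule.

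The correction is to wording only and leaves design, visits and analyses untouched. It still alters protocol text, so it should go through the amendment process in Protocol 15.1 and could be bundled with the next amendment.

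Send the SAP 3.2.1 tolerability wording to the sponsor as a separate query. If the condition is intended, it belongs in 8.1 and wherever the protocol repeats the rule, which needs a sponsor decision and an amendment. If not, delete the phrase from the SAP.

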### **8.3.6 Permitted Study Drug Dose Adjustments and Interruptions**

AK002 dose adjustments are not permitted. The IV infusion may be interrupted, and/or the rate may be reduced by 50%, if a patient experiences an infusion-related reaction. The time the infusion is initiated/concluded (including any interruptions) will be documented in the eCRF. Infusion interruptions and infusion rate reductions should be documented when reporting any infusion-related reaction AEs. If dose is restarted after an interruption, the infusion must be completed within the 8-hour stability window. Administration will be discontinued if, in the opinion of the Investigator, an interrupted infusion cannot be restarted for safety reasons or if the infusion cannot be completed within the 8-hour stability window.

Administration will also be discontinued in any patient experiencing an SAE during the course of the infusion. A lower infusion rate in new subjects will be considered after assessment of safety results and discussion with the Medical Monitor.

Acetaminophen, antihistamines, and, if needed, a glucocorticoid (e.g., 125 mg methylprednisolone IV) may be administered to the patient if the patient experiences reactions that are considered mild to moderate (e.g., itching or a localized rash) at the Investigator's discretion. If a patient experiences signs or symptoms of anaphylaxis, the patient will be treated with standard of care, such as diphenhydramine, acetaminophen, methylprednisolone, epinephrine, and other supportive measures along with cessation of the infusion. As part of the anaphylaxis assessment, a sample of blood should be obtained for plasma histamine and tryptase level within 1 to 2 hours of the onset of the symptoms.

Any missed or altered study drug administrations must be recorded on the Dosage Administration Record eCRF in order to reconstruct an accurate dosing history for each patient.

### **8.3.7 AK002 Accountability**

The site's designated pharmacist will keep accurate and current accounting of the preparation and dose calculation of study drug for each patient, with source, quantities of study medication dispensed, used, and returned. All dosage calculations will be documented in the source documents. A study drug receipt, dispensing, and disposition log will be maintained by the pharmacist on the Investigational Drug Accountability Record. A study monitor will verify entries on these documents throughout the course of the study.

Used study drug vials must be inspected by the study monitor prior to destruction or return to the study drug vendor.

### **8.3.8 Measures of Treatment Compliance**

AK002 will be administered under supervision of the Principal Investigator or Sub-Investigator. The calendar date and 24-hour clock times when the infusion is initiated and concluded, including any interruptions, will be documented in the eCRF.

### **8.3.9 Dietary and Lifestyle Restrictions**

Subjects will refrain from alcohol and strenuous exercise (e.g., heavy lifting, weight training, aerobics) for at least 24 hours prior to each blood collection for clinical laboratory tests. Subjects will fast for at least 8 hours before blood for clinical laboratory tests is obtained.

### **8.3.10 Prohibited Treatments**

Use of the class of treatments displayed in Table 2 is **NOT** allowed after start of screening (Visit 1). The minimum required period without prohibited treatment before Visit 2 is also listed in [Table 2](#).

**Table 2      Prohibited Treatments**

Medication	Minimum Required Period without Medications
Omalizumab	within 2 months of Baseline
H2-antihistamines	7 days prior to Baseline
Routine (daily or every other day during 5 or more consecutive days) doses of systemic corticosteroids	14 days prior to Baseline
Routine (daily or every other day during 5 or more consecutive days) doses of systemic hydroxychloroquine	30 days prior to Baseline
Routine (daily or every other day during 5 or more consecutive days) doses of methotrexate, cyclosporine A, cyclophosphamide, tacrolimus and mycophenolate mofetil	4 weeks or 5 half-lives prior to Baseline
Intravenous immunoglobulin G	30 days prior to Baseline
Plasmapheresis	30 days prior to Baseline
Regular (daily or every other day) doxepin (oral)	14 days prior to Baseline
Inactive vaccination	30 days prior to Baseline
Live attenuated vaccine	30 days prior to Baseline
Leukotriene Antagonists	7 days

If the prohibited treatment was used during the study for any indication, the patient must discontinue use of the prohibited treatment if he/she wishes to continue in the study. If the patient received a live virus vaccination during the study, the patient must discontinue study treatment.

The list of prohibited medications is not considered all inclusive. Medication should be assessed for adherence to the indication and other inclusion/exclusion criteria.

The Investigator should instruct the patient to notify the study site about any new medications he/she takes subsequent to receiving the study drug. All medications and significant non-drug therapies (including physical therapy and blood transfusions) administered following initial study drug treatment, must be listed on the concomitant medications/significant non-drug therapies CRF.

